5.3. Swallowability Assessment for LDV/SOF Placebo Tablets

For subjects in the 12 to <18 and 6 to <12 age groups, swallowability of LDV/SOF placebo tablets will be summarized using the numbers and percentages of subjects in each swallowability category (ie, Able to Swallow, Unable to Swallow).

A by-subject listing of Swallowability of LDV/SOF FDC tablets will be provided by subject ID number in ascending order.

5.4. Palatability of LDV/SOF Oral Granules

For subjects in any age group, dosed with granules, palatability will be assessed by numeric response marked on line between numbers 0-100 (higher scores indicate better taste).

Palatability of LDV/SOF oral granules will be summarized using the numbers and percentages of subjects by age group in the following palatability categories:

- Did Not Taste the Study Drug
- Tasted the Study Drug:
 - Taste score > 60 to 100
 - Taste score 40 to 60
 - Taste score 0 to < 40

A by-subject listing of Palatability of LDV/SOF oral granules will be provided by subject ID number in ascending order.

5.5. Medical History

General medical history (ie, conditions not specific to the disease being studied) data will be collected at screening and listed only. General medical history data will not be coded. A by-subject listing of disease-specific medical history will be provided by subject ID number (in ascending order) and medical history of abnormalities (in chronological order).

6. EFFICACY ANALYSES

6.1. Key Efficacy Endpoint

6.1.1. Definition of the Key Efficacy Endpoint

The key efficacy endpoint is SVR12 defined as HCV RNA < LLOQ (ie, < 15 IU/mL) 12 weeks after discontinuation of all study drugs in the FAS. The COBAS[®] AmpliPrep/COBAS[®] TaqMan[®] HCV Test, v2.0 for use with the High Pure System will be used to measure HCV RNA.

6.1.2. Analysis Methods for the Key Efficacy Endpoint

No inferential statistics will be provided for efficacy endpoints. No statistical comparison will be conducted.

The point estimates of SVR12 rate and 2-sided 95% exact CI based on Clopper-Pearson method will be provided for the SVR12 rate by treatment group and total in each age group {Clopper 1934}.

6.1.3. Subgroup Analysis of the Key Efficacy Endpoint

The point estimates of SVR12 rate and 2-sided 95% exact CIs based on Clopper-Pearson method will be provided for each treatment group within each subgroup specified in Section 3.4 {Clopper 1934}.

A Forest plot will graphically present estimates and 95% confidence intervals of SVR12 rates for each treatment group within each subgroup.

6.2. Secondary Efficacy Endpoints

6.2.1. Definition of Secondary Efficacy Endpoints

Secondary efficacy endpoints include the following:

- The percentage of subjects who attain SVR at 4 and 24 weeks after stopping therapy, defined as HCV RNA < LLOQ (ie, < 15 IU/mL) 4 and 24 weeks after stopping treatment (SVR 4 and SVR 24)
- The percentage of subjects with HCV RNA below LLOQ by study visit
- HCV RNA (\log_{10} IU/mL) and change from baseline in HCV RNA (\log_{10} IU/mL) through end of treatment (EOT)
- The percentage of subjects with virologic failure as the following:

On-treatment virologic failure

- HCV RNA \geq LLOQ after having previously had HCV RNA $<$ LLOQ, while on treatment, confirmed with 2 consecutive values (note, second confirmation value can be posttreatment), or last available on-treatment measurement with no subsequent follow-up values (ie, breakthrough)
- $> 1 \log_{10}$ IU/mL increase in HCV RNA from nadir while on treatment, confirmed with 2 consecutive values (note, second confirmation value can be posttreatment), or last available on-treatment measurement with no subsequent follow-up values (ie, rebound)
- HCV RNA persistently \geq LLOQ through 8 weeks of treatment (ie, nonresponse)

Relapse

- HCV RNA \geq LLOQ during the posttreatment period having achieved HCV RNA $<$ LLOQ at end of treatment, confirmed with 2 consecutive values or last available posttreatment measurement
- The proportion of subjects with ALT normalization (defined as ALT $>$ ULN at baseline and ALT \leq ULN at each visit), presented by study visit.
- Characterization of HCV drug resistance substitutions at baseline, during, and after therapy with LDV/SOF

6.2.2. Analysis Methods for Secondary Efficacy Endpoints

For analyses of HCV RNA $<$ LLOQ by visit while on treatment and during the posttreatment (SVR) follow-up period, subjects will be assigned a value at each visit based on the analysis visit windows specified in Section 3.7.2. Missing values will be imputed based on the categorical imputation rules described in Section 3.5.1. The 2-sided 95% exact confidence interval based on Clopper-Pearson method will be provided for the percentage of subjects with HCV RNA $<$ LLOQ at each visit in each treatment group. The overall category for “HCV RNA $<$ LLOQ” will be split into the following 2 subcategories: “ $<$ LLOQ TND” for subjects with target not detected and “ $<$ LLOQ detected” for subjects with $<$ LLOQ detected in tabular displays.

Graphs for the percentage of subjects with HCV RNA $<$ LLOQ over time during treatment will be displayed.

Summary statistics will be presented for absolute values and change from baseline in HCV RNA (\log_{10} IU/mL) by visit through EOT. Imputation rules described in Section 3.5.1 will be used to assign HCV RNA values for missing values at a visit that are bracketed by “ $<$ LLOQ TND” and/or “ $<$ LLOQ detected”. Otherwise, a missing = excluded analysis will be performed. Plots of the mean \pm SD and median (Q1, Q3) of absolute values and changes from baseline in HCV RNA through EOT will be presented.

For the SVR12 endpoint analysis, a summary table of the number and percentage of subjects with SVR12, virologic failure (VF), and Other will be created. All subjects who achieve SVR12 will be categorized as SVR12. Virologic failure will be descriptively summarized as “on-treatment virologic failure” and relapse (which will be broken down by study drug completed yes/no). Subjects who do not achieve SVR12 and do not meet criteria for VF will be categorized as Other. The denominator for relapse will be the number of subjects who had HCV RNA < LLOQ on their last observed on-treatment HCV RNA measurement; otherwise, the denominator will be the number of subjects in the FAS. Additional summary table will be provided by treatment group defined in [Table 3-3](#) for 3 to < 6 years of age subjects.

A concordance table between SVR12 and SVR24 will be provided by treatment group and total in each age group. Subjects with both observed SVR12 and observed SVR24 data will be included for this analysis.

In addition, a summary table of the number and percentage of subjects with HCV RNA < LLOQ and \geq LLOQ at the posttreatment follow-up visit (observed and imputed, with reasons for imputed) will be provided for each posttreatment follow-up visit. 95% Clopper-Pearson exact CIs will be presented for the overall proportion of subjects with HCV RNA < LLOQ.

Tables for ALT normalization by visit will use similar methodology to the analyses of HCV RNA < LLOQ, but will use a missing = excluded analysis. Only those subjects with ALT greater than the ULN range at baseline (defined as the last ALT value collected prior to first dose of study drug) will be included in the analysis of ALT normalization.

Drug resistant substitutions will be analyzed as part of the Virology Study Report.

6.3. Exploratory Efficacy Endpoints

PPD [REDACTED]

[REDACTED]

[REDACTED]

[REDACTED]

[REDACTED]

[REDACTED]

[REDACTED]

[REDACTED]

[REDACTED]

[REDACTED]

[REDACTED]

PPD

6.4. Changes From Protocol-Specified Efficacy Analyses

There are no changes from protocol-specified efficacy analyses.

7. SAFETY ANALYSES

7.1. Adverse Events and Deaths

7.1.1. Adverse Event Dictionary

Clinical and laboratory adverse events (AEs) will be coded using Medical Dictionary for Regulatory Activities (MedDRA). System organ class (SOC), high-level group term (HLGT), high-level term (HLT), preferred term (PT), and lower-level term (LLT) will be provided in the AE dataset.

7.1.2. Adverse Event Severity

Adverse events are graded by the investigator as Grade 1, 2, 3, or 4 according to toxicity criteria specified in the protocol. The severity grade of events for which the investigator did not record severity will be categorized as “missing” for tabular summaries and data listings and the most severe will be considered (for sorting purpose only) in data presentation.

7.1.3. Relationship of Adverse Events to Study Drug

Related AEs are those for which the investigator selected “Related” on the AE eCRF to the question of “Related to Study Treatment”. Events for which the investigator did not record relationships to study drug will be considered related to study drug for summary purposes. However, by-subject data listings will show the relationship as missing from that captured on the CRF.

7.1.4. Serious Adverse Events

Serious adverse events (SAEs) will be identified and captured as SAEs if AEs met the definitions of SAE specified in the study protocol. Serious adverse events captured and stored in the clinical database will be reconciled with the SAE database from the Gilead Pharmacovigilance and Epidemiology Department before database finalization.

7.1.5. Treatment-Emergent Adverse Events

7.1.5.1. Definition of Treatment Emergent

Treatment-emergent adverse events (TEAEs) are defined as one or both of the following:

- Any AEs with an onset date on or after the study drug start date and no later than 30 days after permanent discontinuation of study drug.
- Any AEs leading to premature discontinuation of study drug.

7.1.5.2. Incomplete Dates

If the onset date of the AE is incomplete, then the month and year (or year alone if month is not recorded) of onset determine whether an AE is treatment emergent, as long as the AE stop date is not prior to the first dose date of study drug. The event is considered treatment emergent if both of the following 2 criteria are met:

- The AE onset and end dates are the same as or after the month and year (or year) of the first dose date of study drug
- The AE onset date is the same as or before the month and year (or year) of the 30th day after the date of the last dose of study drug

An AE with completely missing onset and stop dates, or with the onset date missing and a stop date later than the first dose date of study drug, will be considered to be treatment emergent.

7.1.6. Summaries of Adverse Events and Deaths

A brief high-level summary of TEAEs will be provided by treatment group and by the number and percentage of subjects who had the following: any AE; any AE of Grade 3 or above; any AE of Grade 2 or above; any treatment-related AE; any treatment-related AE of Grade 3 or above; any treatment-related AE of Grade 2 or above; any SAE; any treatment-related SAE; any AE that led to premature discontinuation of any study drug; any AE that led to premature discontinuation of all study drugs; any AE that led to premature discontinuation of LDV/SOF FDC; any AE that led to premature discontinuation of RBV; any AE that led to modification or interruption of any study drug; any AE that led to interruption of LDV/SOF FDC; any AE that led to modification or interruption of RBV. All deaths (including those that are treatment emergent and those that are not treatment emergent) observed during the study will also be summarized and included in this table. Additionally, for subjects 3 to < 6 years of age, a brief high-level summary of TEAEs will be provided by treatment group defined [Table 3-3](#).

Adverse event summaries will provide the number and percentage of subjects with TEAEs by SOC and PT, by treatment group based on the Safety Analysis Set as follows:

- All AEs
- AEs of Grade 3 or above
- AEs of Grade 2 or above
- All treatment-related AEs
- Treatment-related AEs of Grade 3 or above
- Treatment-related AEs of Grade 2 or above
- All SAEs

- All treatment-related SAEs
- AEs leading to premature discontinuation of any study drug
- AEs leading to premature discontinuation of all study drugs
- AEs leading to premature discontinuation of LDV/SOF FDC
- AEs leading to premature discontinuation of RBV
- AEs leading to modification or interruption of any study drug
- AEs leading to interruption of LDV/SOF FDC
- AEs leading to modification or interruption of RBV

Multiple events will be counted only once per subject in each summary. Adverse events will be summarized and listed first in alphabetic order of SOC and then by PT in order of descending incidence of the pooled treatment groups within each SOC. In summaries by severity grade, the most severe grade will be used for those AEs that occurred more than once in an individual subject during the study.

In addition to the above summary tables, TEAEs will be summarized by PT only, in order of descending incidence within the pooled treatment groups for:

- AEs that occurred in at least 5% of subjects within any treatment group
- AEs of Grade 3 or above
- All treatment-related AEs
- All SAEs
- AEs leading to premature discontinuation of any study drug
- AEs leading to premature discontinuation of all study drugs
- AEs leading to premature discontinuation of LDV/SOF FDC
- AEs leading to premature discontinuation of RBV
- AEs leading to modification or interruption of any study drug
- AEs leading to interruption of LDV/SOF FDC
- AEs leading to modification or interruption of RBV

In addition to the by-treatment summaries described above, data listings will be provided for the following:

- All AEs (with a variable indicating whether the event is treatment emergent)
- AEs of Grade 3 or above
- SAEs
- Deaths
- AEs leading to premature discontinuation of any study drug
- AEs leading to modification or interruption of any study drug

7.2. Laboratory Evaluations

Laboratory data collected during the study will be analyzed and summarized using both quantitative and qualitative methods. Summaries of laboratory data will be provided for the Safety Analysis Set and will include data collected up to the last dose of study drug plus 30 days for subjects who have permanently discontinued study drug or all available data at the time of the database snapshot for subjects those who were ongoing at the time of an interim analysis. The analysis will be based on values reported in conventional units. When values are below the limit of quantitation, they will be listed as such, and the closest imputed value will be used for the purpose of calculating summary statistics. For example, if “< 0.2” was recorded, a value of 0.1 will be used for the purpose of calculating summary statistics; if “< 0.1” was recorded, a value of 0.09 will be used for the purpose of calculating summary statistics.

A by-subject listing for laboratory test results will be provided by subject ID number and visit in chronological order for hematology, serum chemistry, and urinalysis separately. Values falling outside of the relevant reference range and/or having a severity grade of 1 or higher on the Gilead Grading Scale for Severity of Adverse Events and Laboratory Abnormalities will be flagged in the data listings, as appropriate.

No inferential statistics will be generated.

7.2.1. Summaries of Numeric Laboratory Results

Descriptive statistics (n, mean, SD, median, Q1, Q3, minimum, and maximum) will be provided by treatment group for ALT, AST, total bilirubin, alkaline phosphatase, hemoglobin, reticulocytes, white blood cell (WBC), neutrophils, lymphocytes, platelets, and INR as follows:

- Baseline values
- Values at each postbaseline analysis window
- Change from baseline at each postbaseline analysis window

A baseline laboratory value will be defined as the final assessment performed on or prior to the date/time of first dose of study drug. Change from baseline to a postbaseline visit will be defined as the visit value minus the baseline value. The mean, median, Q1, Q3, minimum, and maximum will be displayed to the reported number of digits; SD to the reported number of digits plus 1.

Median (Q1, Q3) of the observed values for these laboratory parameters will be plotted using a line plot by treatment group and visit.

In the case of multiple values in an analysis window, data will be selected for analysis as described in Section 3.7.3 (Selection of Data in the Event of Multiple Records in a Window).

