1.5. Rationale for Dose Selection of LDV/SOF FDC

Ledipasvir /Sofosbuvir (90 mg/ 400 mg) fixed-dose combination tablet +/- RBV has demonstrated favorable safety and efficacy profiles in over 3000 HCV-infected subjects across different patient populations in Phase 2 and 3 clinical trials. These doses represent the marketed dose of a ledipasvir/sofosbuvir fixed-dose combination tablet for the treatment of HCV-infection in adults.

[figure not shown]
Selection of doses of LDV/SOF FDC +/- RBV for adolescents and younger age groups will target systemic exposures similar to those observed in adults at the proposed marketed dose. LDV and SOF are substrates for efflux drug transporters P-glycoprotein (P-gp) and breast cancer resistance protein (BCRP). LDV is also a subject to slow oxidative metabolism via an unknown mechanism. SOF is extensively metabolized to the pharmacologically active nucleoside analog phosphate. The activation pathway involves hydrolysis by intestinal and hepatically expressed carboxylesterase (CES1) and Cathepsin A (CatA) enzymes {Yang 2009, Zhu 2009}. SOF is also converted to GS-331007, an inactive circulating metabolite, which is eliminated renally by active tubular secretion and glomerular filtration. Available data suggest comparable hepatic expression of CES1 in adolescents and adults with modestly decreased expression in children. However, little is known about the developmental regulation of Pgp, CES, and CatA. When adjusted for

[figure not shown]
BSA, the processes of active secretion and glomerular filtration approximate adult activity by 6 to 12 months of age {[Kearns 2003](#)}.

The adult clinical dose of LDV/SOF FDC (90 mg/ 400 mg) was evaluated in adolescent subjects (12 to <18 years old) while a lower LDV/SOF FDC (45 mg/ 200 mg) is being evaluated in children (6 to <12 years old), respectively. The appropriateness of these doses are supported by data from the Cohort 1 and Cohort 2 PK Lead-in Phase which demonstrated comparable LDV, SOF, and GS-331007 exposures in adolescent subjects who received LDV/SOF FDC (90 mg/ 400 mg) or children who received LDV/SOF FDC (45 mg/ 200 mg) compared to adult subjects in Phase 2/3 population PK analyses.

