4.3. Exclusion Criteria

Subjects who meet *any* of the following exclusion criteria are not to be enrolled in this study.

- 1) Pregnant or lactating subjects
- 2) Sexually-active males or females of childbearing potential who are not willing to use an effective method of contraception during the study (see [Appendix 5](#) for further details)
- 3) Treatment-naïve subjects with GT-3 HCV infection as determined at Screening. Treatment naïve is defined by no prior exposure to any IFN, RBV, or other approved or experimental HCV-specific DAA agent
- 4) Decompensated liver disease defined as INR $>$ 1.2 \times ULN, platelets $<$ 50,000/mm³, serum albumin $<$ 3.5 g/dL, or prior history of clinical hepatic decompensation (e.g., ascites, jaundice, encephalopathy, variceal hemorrhage)
- 5) Chronic liver disease of a non-HCV etiology (e.g., hemochromatosis, Wilson's disease, alpha-1 antitrypsin deficiency)

- 6) α -fetoprotein > 50 ng/mL
- 7) Serum creatinine > 1.5 mg/dL
- 8) Estimated glomerular filtration rate < 90 mL/min/1.73m², as calculated by the Schwartz Formula
- 9) Evidence of hepatocellular carcinoma (HCC) or other malignancy (with the exception of certain resolved skin cancers)
- 10) Co-infection with HIV, acute HAV, or HBV (i.e. Hepatitis B Surface Ag positive at screening)
- 11) Significant cardiovascular, pulmonary, or neurological disease
- 12) Evidence of a gastrointestinal malabsorption syndrome that may interfere with absorption of orally administered medications
- 13) History of solid organ or bone marrow transplantation
- 14) Chronic daily non-steroidal anti-inflammatory drug therapy
- 15) Systemic corticosteroid use for > 2 weeks (pulmonary/nasal administration is permitted)
- 16) Investigational agents taken within the past 28 days (except with the expressed approval of the Sponsor)
- 17) Clinically-relevant alcohol or drug abuse within 12 months of screening. A positive drug screen will exclude subjects unless it can be explained by a prescribed medication; the diagnosis and prescription must be approved by the investigator
- 18) Known hypersensitivity to the study drug, the metabolites, or formulation excipients
- 19) Any other condition (including alcohol or substance abuse) or prior therapy that, in the opinion of the Investigator, would make the subject unsuitable for the study or unable to comply with dosing requirements
- 20) Use of any prohibited concomitant medications as described in Section 5.6

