6.6.9. Estimated Glomerular Filtration Rate (GFR)

Estimated Glomerular Filtration Rate (GFR) using Schwartz Formula ($\text{mL}/\text{min}/1.73\text{m}^2$) = $k \times L/\text{Scr}$ [(k is a proportionality constant, for adolescent females ≥ 12 years old is 0.55; for adolescent males ≥ 12 years old is 0.70; and for female and male children 3 to < 12 years old is 0.55); L is height in centimeters (cm); and S_{cr} is serum creatinine (mg/dL)]

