Blood Urea Nitrogen	1.25 to 2.50 × ULN	> 2.50 to 5.00 × ULN	> 5.00 to 10.00 × ULN	> 10.00 × ULN
Hyperuricemia	>ULN to 10.0 mg/dL >ULN to 597 μmol/L	> 10.0 to 12.0 mg/dL > 597 to 716 μmol/L	> 12.0 to 15.0 mg/dL > 716 to 895 μmol/L	> 15.0 mg/dL > 895 μmol/L
Hypouricemia Adult and Pediatric ≥ 1 year	1.5 mg/dL to < LLN 87 μmol/L to < LLN	1.0 to < 1.5 mg/dL 57 to < 87 μmol/L	0.5 to < 1.0 mg/dL 27 to < 57 μmol/L	< 0.5 mg/dL < 27 μmol/L
Infant < 1 Year	N/A	1.0 mg/dl to <LLN- 57 μmol to <LLN	0.5 to < 1.0 mg/dL 27 to < 57 μmol/L	< 0.5 mg/dL < 27 μmol/L
Creatinine**	> 1.50 to 2.00 mg/dL > 133 to 177 μmol/L	> 2.00 to 3.00 mg/dL > 177 to 265 μmol/L	> 3.00 to 6.00 mg/dL > 265 to 530 μmol/L	> 6.00 mg/dL > 530 μmol/L

CHEMISTRY				
	Grade 1	Grade 2	Grade 3	Grade 4
Bicarbonate Adult and Pediatric ≥ 4 Years	16.0 mEq/L to < LLN 16.0 mmol/L to < LLN	11.0 to < 16.0 mEq/L 11.0 to < 16.0 mmol/L	8.0 to < 11.0 mEq/L 8.0 to < 11.0 mmol/L	< 8.0 mEq/L < 8.0 mmol/L
Pediatric < 4 Years	NA	11.0 mEq/L to <LLN 11.0 mmol/L to <LLN	8.0 to < 11.0 mEq/L 8.0 to < 11.0 mmol/L	< 8.0 mEq/L < 8.0 mmol/L
Triglycerides (Fasting)	NA	500 to 750 mg/dL 5.64–8.47 mmol/L	> 750 to 1200 mg/dL > 8.47–13.55 mmol/L	> 1200 mg/dL > 13.55 mmol/L
LDL (Fasting) Adult	130 to 160 mg/dL 3.35 to 4.15 mmol/L	>160 to 190 mg/dL >4.15 to 4.92 mmol/L	> 190 mg/dL >4.92 mmol/L	NA
LDL (Fasting) Pediatric >2 to <18 years	110 to 130 mg/dL 2.84 to 3.37 mmol/L	>130 to 190 mg/dL >3.37 to 4.92 mmol/L	> 190 mg/dL >4.92 mmol/L	NA
Hypercholesterolemia (Fasting)	200 to 239 mg/dL 5.16 to 6.19 mmol/L	> 239 to 300 mg/dL > 6.19 to 7.77 mmol/L	> 300 mg/dL > 7.77 mmol/L	NA
Pediatric < 18 Years	170 to 199 mg/dL 4.39 to 5.15 mmol/L	> 199 to 300 mg/dL > 5.15 to 7.77 mmol/L	> 300 mg/dL > 7.77 mmol/L	NA
Creatine Kinase	3.0 to < 6.0 × ULN	6.0 to < 10.0 × ULN	10.0 to < 20.0 × ULN	≥ 20.0 × ULN

* Calcium should be corrected for albumin if albumin is < 4.0 g/dL

** An overlap between the Grade 1 scale and the Lab's normal range for creatinine may result for Male subjects >70 yrs. Please follow the Gilead convention of grading any result within the LLN and ULN a 0.

ENZYMES				
	Grade 1	Grade 2	Grade 3	Grade 4
AST (SGOT)	1.25 to 2.50 × ULN	> 2.50 to 5.00 × ULN	> 5.00 to 10.00 × ULN	> 10.00 × ULN
ALT (SGPT)	1.25 to 2.50 × ULN	> 2.50 to 5.00 × ULN	> 5.00 to 10.00 × ULN	> 10.00 × ULN
GGT	1.25 to 2.50 × ULN	> 2.50 to 5.00 × ULN	> 5.00 to 10.00 × ULN	> 10.00 × ULN

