7.2.2. Graded Laboratory Values

The Gilead Grading Scale for Severity of Adverse Events and Laboratory Abnormalities will be used for assigning toxicity grades to laboratory results for analysis as Grade 0, Grade 1, Grade 2, Grade 3, or Grade 4. Grade 0 includes all values that do not meet the criteria for an abnormality of at least Grade 1. Some laboratory tests have criteria for both increased and decreased levels; analyses for each direction (ie, increased, decreased) will be presented separately.

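### After baseline, the only tabulated laboratory measure of filtration is a creatinine grade with no paediatric band, so no planned laboratory summary would show a moderate fall in eGFR in small children

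*SAP*

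**What the plan says.** SAP 7.2.1 gives baseline, by-visit values and change from baseline for ALT, AST, total bilirubin, alkaline phosphatase, "hemoglobin, reticulocytes, white blood cell (WBC), neutrophils, lymphocytes, platelets, and INR as follows". Creatinine and eGFR are absent. SAP 5.2 computes Schwartz eGFR, but as a baseline characteristic only.

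SAP 7.2.2 tabulates each subject's worst post-baseline grade per analyte, and "Grade 0 includes all values that do not meet the criteria for an abnormality of at least Grade 1". In Protocol Appendix 3 creatinine has a single row whose Grade 1 is "> 1.50 to 2.00 mg/dL". The footnote to that row mentions age once, for an overlap with the normal range that "may result for Male subjects >70 yrs". Rows for phosphate, bicarbonate, LDL, cholesterol and albumin do have age bands.

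Protocol 4.3 excludes on two renal criteria, "Serum creatinine > 1.5 mg/dL" and "Estimated glomerular filtration rate < 90 mL/min/1.73m" (squared). Protocol 6.6.9 defines eGFR as k × height / creatinine; k "for female and male children 3 to < 12 years old is 0.55", also 0.55 for girls of 12 and over, and 0.70 for boys of 12 and over.

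SAP 7.2 also plans a by-subject listing of all serum chemistry, with flags for values that are graded or outside the reference range.

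**The concern.** Safety and tolerability is the primary objective of the Treatment Phase, and about 120 of the 220 planned subjects are 3 to <12 years old. The protocol treats paediatric filtration as important enough to screen on, yet no summary follows it afterwards. What remains in the tables is a creatinine grade fixed at a concentration far above what a small child with an eligible eGFR can have. A graded table with no creatinine abnormalities in the younger group could then be reported as evidence of stable renal function, when a substantial fall would have produced the same table.

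Kidney function has some bearing here because GS-331007 is "an inactive circulating metabolite, which is eliminated renally by active tubular secretion and glomerular filtration". That makes filtration relevant to exposure; it is not evidence of kidney harm.

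**Working it through.** The plan states no figure on this point, so there is nothing to reproduce first. The check applies the trial's own formula to its own threshold.

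**Inputs from the documents.** Highest Grade 0 creatinine: 1.50 mg/dL (Appendix 3). k = 0.55 for ages 3 to <12 (Protocol 6.6.9). Lowest eligible eGFR: 90 mL/min/1.73m² (Protocol 4.3).

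**Assumptions.** The documents give no heights or baseline eGFRs. Heights of 90 to 150 cm are used for this age group, with a baseline eGFR of 90 (the entry limit) or 120. Height is held fixed within a child.

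**Step 1: which entry criterion binds.** With k = 0.55, a creatinine of 1.5 mg/dL is compatible with eGFR 90 only at a height of 90 × 1.5 / 0.55 = 245 cm. At all realistic heights the eGFR criterion is the stricter one. The Grade 1 threshold is the same 1.5 mg/dL.

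**Step 2: eGFR at the highest Grade 0 value.** eGFR = 0.55 × height / 1.50. Creatinine at entry with eGFR 90 = 0.55 × height / 90. Percent loss = 1 − (eGFR at 1.50) / (baseline eGFR).

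| Height (cm) | Creatinine at eGFR 90 (mg/dL) | eGFR at 1.50 mg/dL | Ungraded loss from 90 | Ungraded loss from 120 |
|---|---|---|---|---|
| 90 | 0.55 | 33.0 | 63.3% | 72.5% |
| 100 | 0.61 | 36.7 | 59.3% | 69.4% |
| 110 | 0.67 | 40.3 | 55.2% | 66.4% |
| 120 | 0.73 | 44.0 | 51.1% | 63.3% |
| 130 | 0.79 | 47.7 | 47.0% | 60.3% |
| 140 | 0.86 | 51.3 | 43.0% | 57.2% |
| 150 | 0.92 | 55.0 | 38.9% | 54.2% |

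**Step 3: when more than half is lost without a grade.** From eGFR 90, half is 45, so the boundary height is 45 × 1.50 / 0.55 = 122.7 cm. In general the condition is baseline eGFR > 2 × 0.55 × height / 1.50 = 0.733 × height: above 102.7 at 140 cm, above 110 at 150 cm. At fixed height this is the same as a baseline creatinine below 0.75 mg/dL.

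**Step 4: adolescents.** A girl of 12 or over at an assumed 160 cm reaches 0.55 × 160 / 1.50 = 58.7 while still Grade 0, a loss of 34.8% from 90 or 51.1% from 120. A boy of 12 or over at an assumed 175 cm reaches 0.70 × 175 / 1.50 = 81.7, a loss of 9.3% from 90.

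**Step 5: other planned output.** The separate listing of Grade 3 or above abnormalities needs creatinine above 3.00 mg/dL, which at 95 cm is eGFR 0.55 × 95 / 3.00 = 17.4. In the study schedules, scheduled urinalysis after baseline occurs only at PK Lead-in Day 10, and it does not measure filtration.

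**The case against.** Several points on the other side stand.

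- A reader might infer that renal safety after baseline is measured only by the grade. The documents do not support that. The SAP 7.2 chemistry listing shows every creatinine value and flags those outside the reference range, although it is not stated whether that range is age-specific. Under Protocol 8.1.3, abnormalities that need intervention or change study drug must be recorded as adverse events, and those are tabulated. A DMC also reviews safety. None of this is a summary of filtration, and Protocol 8.1.3 keeps laboratory changes without clinical significance out of the adverse event tables.
- A reader might also infer that the graded table would look clean however far renal function fell. It would not: any creatinine above 1.50 mg/dL is graded.
- A loss of more than half is not available to every child. It depends on height and baseline eGFR, and both are assumed here.
- The SAP breaks no commitment. Protocol 9.5.3 promises summaries of selected laboratory data and does not name creatinine.
- The documents name no renal signal. GS-331007 is described as inactive, and Protocol 9.4 reports no clinically significant exposure-safety relationship for GS-331007 or SOF. The primary safety endpoint is adverse events leading to permanent discontinuation, and renal function is not a named secondary endpoint.

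These points limit the claim to what the tables can show. They do not supply a summary that would reveal a moderate decline.

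**Conclusion.** The point holds as a gap in the planned tables. The worst creatinine grade is the only tabulated laboratory measure of filtration after baseline, and its threshold has no paediatric band. A child with k = 0.55 remains Grade 0 down to an eGFR of 33 at 90 cm or 55 at 150 cm. From the entry limit of 90, a loss of more than half goes ungraded below about 123 cm; in taller children it does so when baseline eGFR exceeds about 0.733 times height.

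The gap is widest in the youngest children. It should not be read as confined to them, because girls of 12 and over use the same k. Nor should it be read as suggesting renal toxicity: the conclusion is that an absence of creatinine grades in small children would say little about filtration. The figures rest on the Schwartz formula as the protocol gives it and on the assumed heights and baselines. The change should be made, since it serves the primary safety objective and uses data already collected.

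**What to change.** 1. Add serum creatinine and Schwartz eGFR (value and change from baseline, by visit) to the analytes in SAP 7.2.1.
2. Add one table by age group of the largest on-treatment percent decline in eGFR, or of the lowest on-treatment eGFR relative to the entry limit of 90.
3. Keep the graded table, with a footnote that its creatinine threshold is not age-adjusted.

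The cost is SAP wording and one or two extra descriptive tables. Creatinine is in the chemistry panel (Protocol 6.6.1) drawn at every on-treatment visit, and height is measured at each visit (Protocol 6.6.5). No new data and no change to clinical management are involved.
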